## Abstract

**Background:** During surgery, bacteria in the air in the operating room (OR) is considered a cause of periprosthetic joint infection (PJI). Previously, turbulent airflow (TAF) has been used in ORs. Later, laminar airflow (LAF) has been developed, which minimize the number of colony forming units in the air. However, most studies show no benefit of LAF regarding PJI incidence.

**Aim:** To evaluate the association of LAF versus TAF ventilation on primary PJIs in 90 and 365 days in total hip arthroplasties (THAs) using the Danish hip arthroplasty register (DHR) and the Danish microbiology register (MiBa)

**Methods:** All THAs performed in Denmark in 2010-2020 are identified in DHR. Through DHR, revisions and type of ventilation system is identified. PJI is defined using a validated method combining MiBa with DHR, where infection is defined as two or more positive identical bacteria cultures or is registered by the surgeon as PJI. The risk of PJI s in THAs performed in TAF are compared with THAs performed in LAF using Cox regression models adjusting for confounders.

**Use and relevance:** PJIs are extremely costly and cause a significant morbidity and mortality for the patient. When constructing or renovating a hospital, it is crucial to choose a ventilation system that minimizes PJIs, while being cost-efficient. Previous studies on LAF vs TAF are based on data from national registers. Since registration of PJI is reported immediately to DHR and other arthroplasty registers after surgery, the microbiology results are not taken into consideration when the revision cause is reported. This study is novel, because it gives a more accurate picture of the PJI incidence and can be part in guiding the decisions when renovating or designing new hospitals, in order to decrease the risk of PJI.

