## Data sources

**The Danish Civil Registration System (Centrale Person Register, CPR)** contains information including vital status and time of emigration on all Danish residents (33). All Danish residents and citizens are assigned a unique and permanent individual identification number (CPR number) at birth or upon immigration. It enables an unambiguous linkage between different registers and allows an individual follow-up over time (34).

**The Danish National Patient Register (NPR)** collects data of all Danish residents contact to a public hospital, including date, performed examinations or surgical procedures and diagnosis, classified by International Classification of Diseases (ICD) (35). The data includes both outpatient and inpatient contacts and is linked with the patient's CPR number (36).

**The Danish Hip Arthroplasty Register (DHR)** collects data including type of OR ventilation from all THAs performed in Denmark, including primary THAs as well as revisions (37). It is mandatory for all surgeons performing THAs to report to the register, which results in high completeness. The data is previously validated (38). In the case of a revision, the surgeon reports the indication immediately after surgery (39). The revisions performed within 90 and 365 days are located in the DHR, which also contains information from the NPR about revisions.

**The Danish Microbiology Database (MiBa)** automatically collects all microbiology results from all departments of clinical microbiology in Denmark since 2010, which are then stored electronically using the patient's CPR number as patient identifier (40). The register completeness is previously validated (41). The data will more specifically be extracted from the Healthcare-Associated Infections Database – HAIBA, a part of MiBa.

**The Danish National Prescription Register (DNPR)** collects detailed information on redeemed prescriptions in Denmark since 1995. It is previously validated and has a high degree of completeness and is frequently used in epidemiological research (42).

**Income Statistics Register** – The register contains income data on more than 160 variables including salaries and savings of people with a Danish income and is widely used in research. Each individual is identified with an unambiguous CPR number (43).

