## Variables

The investigators will look at several variables and adjust for these where needed. The variables obtained from DHR is body mass index (BMI), age, gender, time of surgery, diagnosis, type of prosthesis and fixation method, whether cement is used and if it contains antibiotics, previous operations on the same hip and ASA score. ASA score and BMI are only available from 2017 and onwards in DHR.

From NPR, concomitant diagnoses will be obtained to produce an Elixhauser comorbidity score, and socioeconomic factors, such as income and education will be obtained from the Danish Income Statistics Register and Education Register.

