## Methods

The data is reported according to the RECORD guidelines (45) and is stored in the servers of Statistics Denmark, where the data will be analyzed.

Study population:

All people  $\geq 18$  years receiving a primary total hip arthroplasty in Denmark between 01.01.2010-31.12.2020 registered in DHR are included. Patients receiving a THA due to a hip tumor or metastasis are excluded, as well as patients with erroneous registration in DHR.

Exposure:

Surgery performed in an OR with LAF compared with surgery in an OR with TAF.

Follow-up:

Follow-up starts on the operation day and ends 365 days postoperatively. Follow-up is also ended at time of any revision, death or emigration.

Null hypothesis:

There is no difference in the risk of PJIs after a THA performed in a LAF OR as opposed to in a TAF OR.

Alternative hypothesis:

There is a lower or higher risk of PJIs after a THA performed in a LAF OR as opposed to in a TAF OR.

Endpoints:

*Primary endpoint:*

Revision due to infection, measured at t=90 days and t=365 days. Revision is defined as the first surgical intervention in the same hip after a primary THA with debridement, replacement, or removal of prosthetic parts.

A follow-up time of 90 and 365 days respectively is chosen, since 90 days is the recommended surveillance period in the United States and is traditionally the limit between early and late infections, whereas it is important to have a follow up of a year not to miss up to 20 % of the infections (46,47). At 1 year, 80-90 % of the surgically requiring infections that will occur in the lifetime of the hip prosthesis have taken place. After 1 year, the infection rate drastically decreases and is less likely to be due to contamination during surgery (30,47).

PJI is considered present when at least one of the following two criteria exists.

1. Two or more intraoperative deep-tissue samples of the same bacteria, isolated from at least three deep-tissue samples.
2. Deep infection is reported to DHR by the surgeon upon revision surgery.

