#### Statistical analysis:

Descriptive results for continuous variables will be shown as mean(SD)/median(range) depending on the distribution of the variables. Categorical variables will be presented using frequencies and percentages. Persons operated in LAF and TAF ORs are compared using t-tests/Wilcoxon-tests and chi-square tests, respectively. This is supplemented with cumulative incidence plots showing risk of infection (primary outcome) for LAF and TAF, regarding revision due to other causes and death as competing events. The two groups are compared using Grays test. To fulfill the requirements at Statistics Denmark about data on individual persons, a smooth curve is used to make the plot rather than the statistical correct step-function. Information at time 90 and 365 days after the operation will be presented. This type of plot will be used for all endpoints.

For the primary endpoint, two Cox regression analyses will be performed with the time to PJI as outcome. One model will only cover the first 90 days of follow-up, the other will cover all 365 days of follow-up. Censoring is made at time of revision due to other causes than PJI, death, emigration, and end of follow-up (365 days after operation), whichever comes first. Bilateral THA will be included in the model as two observations with inclusion of a time-dependent variable conditioning on the status of the other hip (53). A robust sandwich covariance matrix estimate is used to account for the intrapersonal dependence.

The model will include the following potential confounders:

Education, age, comorbidities, gender, previous hip surgery, primary diagnosis, type of cement, type of fixation, year of surgery, income and duration of surgery. ASA and BMI will be adjusted for in sensitivity analysis c). A direct acyclic graph is used when determining the variables needed to adjust for.

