The linearity assumption for continuous confounders is checked by including these as cubic splines with 3 to 7 knots and using the model with lowest AIC, as suggested by Harrell (54). The proportional hazards assumption for the Cox-regression models is assessed using plots for the cumulative sum of martingale residuals. If the assumption is violated for the exposure (LAF/TAF), the time-axis will be split into smaller parts in which the assumption is fulfilled, and a separate Cox regression is made for each part. If the proportional hazard assumption is violated for confounders, time-dependent covariates is used for these.

Similar Cox-regression models will be used to analyze both secondary endpoints, as well as for the sensitivity analysis of the primary endpoint.

The assumptions of proportional hazards for these endpoints are checked as described for the model for the primary endpoint.

All tests will be two-sided and a p-value of  $<0.05$  will be considered statistically significant. Statistical analysis will be conducted using SAS version 9.4 (SAS Institute Inc.).

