## Perspectives

When constructing or renovating a hospital, it is crucial to choose a ventilation system that minimizes PJIs, while being cost-efficient. Previous studies on LAF vs TAF are based on data from national registers. Since registration of PJI is reported immediately to DHR and other registers after surgery, the microbiology results are not taken into consideration when the revision cause is reported. This study is novel, because it gives a more accurate picture of the PJI incidence and can be part in guiding the decisions when renovating or designing new hospitals, in order to decrease the risk of PJI.

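### The Cox models allow for dependence within a person but not within a hospital, so the LAF/TAF intervals are too narrow if both PJI risk and LAF use differ between hospitals

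*Combined protocol and SAP*

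**What the plan says.** The exposure is defined under Methods at the level of the operating room: "Surgery performed in an OR with LAF compared with surgery in an OR with TAF". The Abstract states the decision that the study should inform: "When constructing or renovating a hospital, it is crucial to choose a ventilation system that minimizes PJIs, while being cost-efficient". Perspectives repeats it. Under Data sources, the Danish Hip Arthroplasty Register (DHR) "collects data including type of OR ventilation from all THAs performed in Denmark", so ventilation is recorded for each operation and may vary within a hospital or change during 2010-2020.

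The Statistical analysis section enters bilateral hips as two observations and gives the robust variance one purpose: "A robust sandwich covariance matrix estimate is used to account for the intrapersonal dependence". The planned confounders are "Education, age, comorbidities, gender, previous hip surgery, primary diagnosis, type of cement, type of fixation, year of surgery, income and duration of surgery". None of the eleven is hospital, department, operating room or surgeon. The model type then carries over: "Similar Cox-regression models will be used to analyze both secondary endpoints, as well as for the sensitivity analysis of the primary endpoint". Nowhere do the documents plan a hospital stratum, random effect, frailty or hospital-level clustering. Gray's test is planned with no stated allowance for clustering. All tests are two-sided at 5%.

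**The concern.** Patients operated on in one hospital may share both the ventilation system and unmeasured conditions that affect infection. Those patients are then not independent observations on the ventilation contrast. A variance clustered on the person handles the small clusters (two hips) and leaves out the large ones (all patients of a hospital), which is where the exposure may be shared.

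Two conditions must both hold for this to matter: PJI risk differs between hospitals beyond the listed covariates, and the LAF share differs between hospitals. Both are plausible, but the documents give no data on either. If both hold, a chance difference between hospitals could be read as a ventilation effect, or a null result could look more precise than it is. Either error matters in a study meant to guide hospital building.

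This point concerns precision. Whether hospital-level confounding also biases the hazard ratio is a separate question that the documents do not settle.

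**Working it through.** The plan states no sample size, event count or power, so it has no figure of its own to reproduce.

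**Inputs from the documents**
- Two-sided level 0.05, critical value 1.96 (Statistical analysis).
- One-year PJI incidence 0.57-0.80%, with the true figure about 40% higher (Rationale and background): 0.57 × 1.4 = 0.80% and 0.80 × 1.4 = 1.12%.
- Sensitivity analysis c uses 2017-2020, which is 4 of the 11 years.

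**Assumed, not in the documents**
- 100,000 hips, so 800 to 1,120 events; D = 1,000 is used below.
- K = 45 hospitals of equal size, with half the hips in LAF.
- SD of the residual hospital log-hazard of 0.1, 0.2 or 0.3.
- s, the share of exposure variance that lies between hospitals: 1 means ventilation is constant within hospital, 0 means the LAF share is equal everywhere.

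**Formula.** With independent observations the variance of the log hazard ratio is about 4/D. Hospital variation adds about s × 4 × SD²/K. Hence

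ratio of true to planned SE = √(1 + s·D·SD²/K), and type I error = 2 × [1 − Φ(1.96/ratio)].

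For s = 1 and SD = 0.2: 1,000 × 0.04/45 = 0.889; √1.889 = 1.374; 1.96/1.374 = 1.426; type I error 15.4%.

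| s | SE ratio, SD 0.2 | Type I error, SD 0.1 | SD 0.2 | SD 0.3 |
|---|---|---|---|---|
| 1 | 1.374 | 7.6% | 15.4% | 25.8% |
| 0.5 | 1.202 | 6.3% | 10.3% | 16.6% |
| 0.25 | 1.106 | 5.6% | 7.6% | 11.0% |
| 0.1 | 1.043 | 5.3% | 6.0% | 7.4% |
| 0 | 1 | 5% | 5% | 5% |

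**Other assumed sizes at SD 0.2** (s = 1 / 0.5 / 0.1)
- K = 30: 19.9 / 12.9 / 6.6%. K = 60: 12.9 / 9.0 / 5.8%.
- D = 800: 13.4 / 9.2 / 5.8%. D = 1,120: 16.5 / 10.9 / 6.2%.
- Sensitivity analysis c, D = 1,000 × 4/11 ≈ 364: 8.8 / 6.9 / 5.4%, if s and SD are unchanged.

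**Effect on an interval.** The planned SE is √(4/1,000) = 0.0632, so an estimate of 1.00 would be reported with limits exp(±1.96 × 0.0632) = 0.88 to 1.13. With s = 1 and SD 0.2 the true SE is 0.0632 × 1.374 = 0.0869, and the limits should be about 0.84 to 1.19.

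**Simulation with unequal hospitals.** Rare-event rate ratios approximated the Cox model, with no covariates and no bilateral hips, 45 hospitals, a coefficient of variation of hospital size of 0.7, and 10,000 replicates per setting. Type I error of the planned test at SD 0.1 / 0.2 / 0.3:
- ventilation constant within hospital: 8.7 / 20.0 / 32.4%
- half of exposure variance between hospitals: 7.0 / 12.5 / 21.3%
- a tenth between hospitals: 5.3 / 6.4 / 8.6%
- equal LAF share everywhere: 4.7 / 4.9 / 5.2%

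With no hospital variation in risk it was 4.6-5.1%. Most of these figures exceed the formula's because unequal hospital sizes make the effect larger. The hospital-clustered test with a t(44) reference gave 4.9-7.3% over all settings.

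A second simulation used 60,000 or 90,000 hips and 30 or 50 hospitals of unequal size, about 60% LAF and a one-year risk of 0.96%. At SD 0.2 the planned test had 13.5-21.2% with all-or-none LAF by hospital and 9.1-14.4% with a partly varying share. It stayed at 4.2-6.2% when either condition failed. Hospital clustering without a small-sample correction gave 5.6-9.1% where both conditions held.

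**The case against.** The strongest objection is that the size rests wholly on assumptions. The documents give no number of hips or hospitals, no LAF share and no between-hospital SD. Ventilation is recorded per operation, so hospitals with both systems are possible. With a tenth of the exposure variance between hospitals and SD 0.1, the formula gives 5.3%, which is negligible. The SD must also be what remains after adjustment, and covariates such as fixation, cement, year, diagnosis and duration of surgery may absorb part of the hospital differences. All of this stands. It limits what can be said about size but does not remove the omission, because the plan neither argues nor checks that either condition fails.

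Three narrower points also stand.
- The DHR list under Variables begins "The variables obtained from DHR is body mass index (BMI), age, gender, time of surgery, diagnosis, type of prosthesis and fixation method" and names no hospital identifier. It also omits ventilation type and revision indication, which the study needs, so it is not a full extraction list. The evidence for the omission is the model and variance specification.
- A smaller effect in sensitivity analysis c is not assured. A shorter window leaves less time for switching, so s could rise: s = 1 with 364 events gives 8.8%, against 7.6% for s = 0.25 with 1,000 events.
- Gray's test already sits with the descriptive results, so little hangs on it.

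Two defences fail. The planned directed acyclic graph selects confounders; it does not change the variance estimator. Complete national coverage does not remove the problem either, because the results are meant to inform future building decisions.

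**Conclusion.** The concern holds in its conditional form. It is certain from the text that dependence is handled only within a person and that no hospital term is planned. Followed as written, this gives intervals that are too narrow and p-values that are too small if residual PJI risk and the LAF share both vary between hospitals. If either is constant, the planned analysis is about right.

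How large the effect will be is not known. Over the assumed values tabulated above, the formula gives a type I error from 5% to about 26%, and the simulations show that unequal hospital sizes can push it higher. This should be fixed before analysis: the exposure is tied to the facility, results are judged at p < 0.05, and the repair is small.

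**What to change.** **Needed**
- Obtain the hospital identifier with the DHR data. Its availability is assumed here.
- Cluster the sandwich variance on hospital in all Cox models (primary, secondary and sensitivity), with a t reference on the number of hospitals minus 1. Hospital clusters contain the person clusters when both hips were done in the same hospital. If some patients had their hips operated on at different hospitals, use two-way clustering on hospital and person.
- Report how many hospitals used LAF only, TAF only and both, so that readers can judge how far the exposure is shared.

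**Useful addition**
- One sensitivity analysis of the primary endpoint stratified by hospital, which draws on hospitals that had, or switched between, both systems. It also checks for hospital-level confounding, which a clustered variance does not remove.
- State that Gray's test is descriptive.

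**Cost.** One identifier, a changed cluster unit and one extra model. Intervals will widen if hospital variation is real and barely change if it is not. The correction is imperfect with few clusters (4.9-7.3% in the simulation with the t reference). The stratified model is less precise because only hospitals with both systems contribute. Check that the planned software supports two-way clustering with a t reference.

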The definition of PJI is based on the studies by Gundtoft et al. (30,31), where it has been concluded, that the validity of the PJI diagnosis is greatly improved when using these criteria, which are validated specifically for DHR. The original study by Gundtoft et al. used an extensive algorithm to determine if a PJI was present. However, there was no statistically significant difference between the extensive algorithm and a simplified algorithm, that defines a PJI as two or more positive identical bacterial samples (30).

The investigators definition is in line with international consensus (48) and does not differ greatly from the definition made by the European Bone and Joint Infection Society (EBJIS) (49), although erythrocyte sedimentation rate, aspiration of joint fluid, white blood cell count in joint fluid and histological examination of intraoperative tissue biopsies are not routinely used in Denmark. Thus, these criteria are not used. Sinus tract communication with the hip joint or an opening to the hip joint is expected to cause the surgeon to register the diagnosis “infection” in DHR upon revision. Data for this analysis will be extracted from DHR and

HAIBA. For the revision surgery to be registered in HAIBA, at least three biopsies at the revision surgery are required, hence this is a part of the criteria (50).

*Secondary endpoints:*

- 1) Revision registered as aseptic loosening in DHR.
- 2) Any revision registered in DHR.

Aseptic loosening is a separate endpoint, since it has been shown that aseptic loosening might in fact turn out to be a PJI and is thus a point of interest (32,51,52).

*Sensitivity analyses:*

In addition, the following sensitivity analyses will be made:

- a) Alternative outcome: Primary revision registered as PJI or with at least one positive biopsy of a bacterium.
- b) Alternative outcome: Primary revision reported to DHR with at least one positive biopsy of a bacterium AND the prescription of a relevant antibiotic, specified in appendix A.
- c) Analysis for the primary endpoint, but for data collected between 2017-2020, allowing for adjustment for BMI and ASA as possible confounders, as these variables are only registered in this period

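### The primary model has no hospital variable, stratum or cluster, so differences between hospitals can be read as a laminar-airflow effect in either direction, and the confidence interval can be too narrow.

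*Combined protocol and SAP*

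**What the plan says.** The Exposure paragraph under Methods defines the contrast by room: "Surgery performed in an OR with LAF compared with surgery in an OR with TAF". The Abstract places the choice of system with the institution: "When constructing or renovating a hospital, it is crucial to choose a ventilation system that minimizes PJIs". Perspectives repeats this. Under Data sources, the hip register (DHR) "collects data including type of OR ventilation from all THAs performed in Denmark".

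The Statistical analysis section lists the confounders in the Cox model: "Education, age, comorbidities, gender, previous hip surgery, primary diagnosis, type of cement, type of fixation, year of surgery, income and duration of surgery". It adds that "A direct acyclic graph is used when determining the variables needed to adjust for"; the graph is not shown. On dependence it says: "A robust sandwich covariance matrix estimate is used to account for the intrapersonal dependence".

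The Variables section describes the extraction: "The variables obtained from DHR is body mass index (BMI), age, gender, time of surgery, diagnosis, type of prosthesis and fixation method", followed by further patient, implant and cement items. It names no hospital, region, ownership or volume variable.

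Sensitivity analyses a) and b) change the outcome definition. Analysis c) restricts to 2017-2020, "allowing for adjustment for BMI and ASA as possible confounders". The secondary endpoints use similar Cox models.

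**The concern.** If ventilation is chosen by the hospital, the hospital is a natural common cause of exposure and outcome. Hospitals with laminar airflow (LAF) may differ from those with turbulent airflow (TAF) in volume, infection-control routines, or how often at least three deep-tissue samples are taken at revision. The last matters because the culture criterion for prosthetic joint infection (PJI) cannot be met with fewer samples. Nothing in the listed model measures these traits. Calendar year absorbs national trends, not differences between hospitals.

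Two separate errors can follow. A trait spread unevenly over the two systems biases the HR. Even with no systematic imbalance, ordinary variation between hospitals makes the standard error too small, because patients from one hospital share both their baseline risk and, often, their exposure. The same gap carries over to the secondary and sensitivity models. The result is meant to inform hospital construction, so ventilation has to be told apart from the hospital that installed it.

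**Working it through.** The plan gives no sample size, event count, target HR or hospital count, so it has no figure to reproduce. What follows is illustrative.

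**Inputs from the documents.** Registered one-year PJI incidence is 0.57-0.80%, and true incidence is about 40% higher (Rationale and background): 0.57 × 1.4 = 0.798% and 0.80 × 1.4 = 1.12%. Tests are two-sided at 0.05. Sensitivity for PJI is 67% with DHR alone and 90% with microbiology data.

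**Assumed inputs.** Cohort of 80,000-100,000 hips; LAF share 50-70%; 40 hospitals; the trait values and between-hospital SDs below. Events: 80,000 × 0.798% ≈ 640; 100,000 × 0.798% ≈ 800; 100,000 × 1.12% = 1,120.

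**1. Bias in the HR.** For a hospital trait with PJI risk ratio g, present for a share p1 of LAF and p0 of TAF operations, a true HR of 1.00 appears as [1 + p1(g − 1)] / [1 + p0(g − 1)].

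| g | p1 | p0 | Apparent HR | With p1 and p0 exchanged |
|---|---|---|---|---|
| 0.8 | 50% | 40% | 0.90/0.92 = 0.98 | 1.02 |
| 0.7 | 60% | 30% | 0.82/0.91 = 0.90 | 1.11 |
| 0.6 | 70% | 30% | 0.72/0.88 = 0.82 | 1.22 |

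Sampling practice gives a scenario tied to the documents. In the extreme case of hospitals that never take three samples, detected risk falls by about 67/90 = 0.74. At 60% versus 30% this gives 0.847/0.923 = 0.92; at 70% versus 30%, 0.821/0.923 = 0.89.

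**2. Comparison with a just-significant HR.** With D events and LAF share a, the threshold is exp(−1.96/√[D·a(1 − a)]), ignoring clustering.
- D = 640: 0.86 (a = 0.5) and 0.84 (a = 0.7).
- D = 1,120: 0.89 (a = 0.5) and 0.88 (a = 0.7).

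Of the three tabulated scenarios, only 0.82 lies beyond this range. The 0.89 from extreme sampling practice sits at its edge.

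**3. Standard error.** Take 800 events, 70% LAF and 40 equal hospitals each wholly LAF (28) or TAF (12). With between-hospital log-hazard SD τ:
- Model as written: SE = √[1/(800 × 0.7 × 0.3)] = √0.00595 = 0.077.
- Allowing for hospital: SE = √[0.00595 + τ²(1/28 + 1/12)] = √[0.00595 + 0.119τ²].
- True type I error of the model as written: 2[1 − Φ(1.96 × 0.077/SE)].

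| τ | SE allowing for hospital | True type I error |
|---|---|---|
| 0.1 | 0.085 | 7% |
| 0.2 | 0.104 | 14% |
| 0.3 | 0.129 | 24% |

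**The case against.** The documents do not say how LAF and TAF are distributed. Exposure is recorded for each operation, and if many hospitals ran both systems, or switched during 2010-2020, confounding by hospital and the inflation in step 3 would both be smaller. Nor do they say how patients were allocated to rooms. This stands: the size of the problem is unknown, and the single-system assumption in step 3 is unfavourable to the plan.

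Several hospital differences are partly covered. Age, comorbidity, diagnosis, previous surgery, income and education address case mix, with BMI and ASA added in analysis c); type of cement touches on prophylaxis. The surgeon-report criterion needs no biopsy, and any revision, a secondary endpoint, does not depend on cultures. This also stands, but it leaves volume, other infection-control routines and sampling frequency unaddressed.

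The unshown graph might contain a hospital node, and the Variables list is not exhaustive: it omits ventilation type itself. A reader should therefore not infer that the hospital is unavailable or was never considered. Still, the model is specified by a list that contains no hospital term.

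A reader might also infer that hospital differences will be read as a LAF benefit, or that this bias by itself would produce a significant result. Neither is supported. The direction depends on which system the trait accompanies, and only the strongest of the three tabulated scenarios clearly crosses the threshold.

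**Conclusion.** The omission is plain on the text: no hospital variable, stratum or cluster appears in the primary model, the secondary models or sensitivity analyses a) to c). Stable hospital differences can therefore be attributed to ventilation in either direction, and the interval can be too narrow.

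No magnitude can be fixed from the documents. The apparent HRs and the 14% type I error at τ = 0.2 show what is possible, not what is expected. Trait values, cohort size, LAF share, hospital count and τ are all assumptions; only the incidence, the sensitivities and the significance level come from the plan. The standard-error problem needs no systematic imbalance, only between-hospital variation not captured by the covariates. The plan should be changed before analysis.

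**What to change.** 1. Add the reporting hospital to the DHR variable list, assuming the register supplies it, and tabulate LAF and TAF operations by hospital and year. Show the causal graph with hospital as a node.
2. Compute the variance allowing for hospital clustering while keeping within-person dependence. Use two-way clustering, or cluster on hospital and check for persons operated at two hospitals. State a small-cluster safeguard in case hospitals are few.
3. Pre-specify a Cox model stratified by hospital as the named robustness analysis for the primary endpoint. Report how many hospitals and events contribute to the within-hospital contrast.
4. Add public/private status and annual THA volume, computed from the cohort, to the adjustment set. State that these do not capture sampling or prophylaxis practice; the stratified model is what addresses stable differences of that kind.

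The cost is SAP wording, one more extracted variable and modest programming. Intervals will widen, and the stratified model draws only on hospitals with both systems or a change over time, so it may be imprecise.
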